## **Clinical Investigation Plan Summary**

Title	A cross-sectional, interventional, single-arm clinical study for validating the equivalence of Bloomlife MFM-Pro to clinical standard-of-care for fetal heart rate and maternal heart rate when performing antepartum fetal monitoring	
Acronym	NST	
Protocol Number	NST-01-2021-US	
Version	3.0 – 23FEB2022	
Reference number (IRB)	Pro00049843	
Funding	This study is funded by Bloomlife Inc (study sponsor)	

Study Synopsis	Population	Non-laboring pregnant women with singleton pregnancy, at 32 weeks of gestation or more, monitored with Bloomlife MFM-Pro and Cardiotocograph (CTG).
	Investigational Device	Bloomlife MFM-Pro is indicated for monitoring of maternal and fetal physiological parameters during the antepartum period. It is to be used by healthcare professionals in hospitals, clinics, physicians' offices, antepartum rooms, and in the patients' home on the order of a physician.  Bloomlife MFM-Pro is a non-invasive, wireless, external monitoring system used to measure fetal heart rate (fHR), maternal heart rate (mHR), and uterine activity during antepartum (non-stress) testing on pregnant women with a singleton pregnancy.
		The system acquires biopotential signals from abdominal surface electrodes and measures the fetal electrocardiography, maternal electrocardiography and electrohysterography. The sensor also acquires motion data through an accelerometer. It transmits the measured data to the Bloomlife Mobile App and to the Cloud for storage/processing.
	Comparison	Reference device: Cardiotocograph (Philips Avalon FM30 or equivalent)

Objectives	Primary objective:  • To demonstrate equivalence of Bloomlife MFM-Pro to clinical standard-of-care for fetal heart rate and maternal heart rate when performing antepartum fetal monitoring.  Secondary objective:  • To establish the safety of Bloomlife MFM-Pro.  Exploratory objectives:  • To compare measurement reliability of Bloomlife MFM-Pro and CTG in measuring fetal heart rate.  • To compare measurement reliability of Bloomlife MFM-Pro and CTG in measuring maternal heart rate.  • To study the Bloomlife MFM-Pro performance when compared to standard-of-care (CTG) for uterine activity.  • To study the correlation between the Bloomlife MFM-Pro signal quality check result and fetal heart rate quality
Endpoints	Primary endpoints:  Extent of agreement between Bloomlife MFM-Pro and CTG in fetal heart rate (FHR) and maternal heart rate (MHR):  95% LoA for FHR within +/- 10 bpm  95% LoA for MHR within +/- 7 bpm  Regression analysis of MFM-Pro vs CTG for fetal heart rate and maternal heart rate determining if the bias is constant across the range of the measurements.  Secondary endpoints:  Summary tables of recorded adverse events, serious adverse events, adverse device effects, device deficiencies.  Exploratory endpoints:  Percentage of a recording with a FHR for Bloomlife MFM-Pro and for CTG.  Percentage of a recording with a MHR for Bloomlife MFM-Pro and for CTG.  Sensitivity and False Event Rate for uterine contractions annotated by experts based on uterine activity traces measured with Bloomlife MFM-Pro and with CTG.

	
 
Confusion matrix between the signal quality check result (pass or fail) and the recording quality (for the MFM-Pro fetal heart rate signal, over the complete measurement)
 

Design	National, prospective, cross-sectional, interventional, single-arm study.
Number of subjects	Pilot phase: up to 200 enrolled subjects Pivotal phase: up to 60 enrolled subjects
Inclusion criteria	
 
Pregnant woman ≥ 18 years old
 
Gestational age ≥ 32 weeks and 0 days
 
Singleton pregnancy
 
Ability to read and understand English or Spanish
 
Willingness to participate in the study
 

Exclusion criteria	
 
Implanted pacemaker or any other implanted electrical device
 
Plurality higher than 1
 
History of allergies to skin adhesives
 
Irritated or lesioned skin at the Bloomlife MFM-Pro electrodes locations
 
Contraindication to the use of CTG (e.g. due to preterm contractions)
 

Enrolment criteria	A participant is considered enrolled when their eligibility is confirmed, and the signal validation screening test (performed by the Bloomlife MFM-Pro) gives a successful result.
Study duration	Q1 2021 – Q2 2022
Study Procedures	Informed consent: Eligible participants will be asked to sign an informed consent form before any study-specific procedure is performed.  MFM-Pro electrodes connection check & signal quality check: Once the informed consent is signed, participants are asked to sit on a reclined (NST) chair (or lie on a hospital bed).

	The researcher prepares the patient's skin by cleaning it and by using medical skin-prep tape on her belly.  The researcher proceeds with setting up the Bloomlife MFM-Pro system, in parallel with the CTG. The researcher instructs the participant to annotate perceived contractions by pressing a button.
	With this setup, data is collected with both devices, while the Bloomlife MFM-Pro performs an electrode connection check and signal quality check (screening test). This step may take up to 15 minutes. If the electrode connection check fails or the CTG does not capture the MHR/FHR signals, the measurement setup is adjusted as needed (up to three attempts are allowed).
	Study measurement:  If the electrodes connection check and the CTG setup are successful, data is collected with both the Bloomlife MFM-Pro and the CTG monitor for 45 minutes.
	A video of the belly and a picture of the setup may also be taken.
	During the data collection, the researcher uses a custom data visualization interface to visualize data from the CTG and the Bloomlife MFM-Pro, to identify issues with the measurement setup and annotate relevant events in the data collection process.
	At the end of the data collection, the Bloomlife MFM-Pro and CTG tracings are stored in a digital format for analysis.
	After the Bloomlife MFM-Pro data collection, relevant information pertaining to the subject's pregnancy and medical history is collected from her medical records and entered in the eCRF.
	Any adverse event observed during the data collection (signal quality check and measurement) will be recorded by the researcher. Information about other adverse events will be collected from the participant's medical records for 7 days after the measurement.
Statistical Data	Limits of Agreement:
Analysis	For assessing the agreement between the Bloomlife MFM-Pro fetal heart rate (FHR) and a standard of care

	Cardiotocograph (CTG), we plan to estimate the 95% limits of agreement (LoA) according to Bland-Altman, together with 95% confidence intervals (95%CI).
	
 
95% limits of agreement objectives:
 
1. Fetal heart rate the 95% limits of agreement lie within +/- 10 bpm
 
2. Maternal heart rate the 95% limits of agreement lie within +/- 7 bpm.
 

	Linear regression analysis:
	A linear regression analysis assessing the relationship between the bias and the magnitude of measurements will also be performed.
Timeline	Subjects are asked to participate in one data collection performed at the clinic. The data collection requires up to 1.5 hours.
	A follow-up period of 7 days (after the measurement) is used to collect safety information.

Sponsor	Name	Bloom Technologies NV (a daughter company of Bloomlife Inc)
	Address	[name]
	Key personnel	[name], Clinical Studies Manager [name], Clinical Research Associate [name], Clinical advisor [name], COO

During the study, the Sponsor keeps a separate document with an updated list of the Principal Investigator(s) and investigation site(s). The PI and site information is submitted to the IRB at study submission.

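### The exploratory FHR reliability endpoint measures whether a rate is present, not whether it is fetal; report a prespecified check against simultaneous MHR beside it

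*Combined protocol and SAP*

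**What the plan says.** All references are to the Clinical Investigation Plan Summary.

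- **Objectives (exploratory):** "To compare measurement reliability of Bloomlife MFM-Pro and CTG in measuring fetal heart rate", with a parallel objective for maternal heart rate (MHR).
- **Endpoints (exploratory):** "Percentage of a recording with a FHR for Bloomlife MFM-Pro and for CTG". The maternal counterpart is "Percentage of a recording with a MHR for Bloomlife MFM-Pro and for CTG". Neither carries a threshold, and neither defines a valid sample.
- **Investigational Device:** MFM-Pro works from abdominal surface electrodes and "measures the fetal electrocardiography, maternal electrocardiography and electrohysterography".
- **Study Procedures:** if "the CTG does not capture the MHR/FHR signals, the measurement setup is adjusted as needed", with up to three attempts. Once setup succeeds, "data is collected with both the Bloomlife MFM-Pro and the CTG monitor for 45 minutes". Afterwards "the Bloomlife MFM-Pro and CTG tracings are stored in a digital format for analysis".
- **Endpoints (primary):** the stated accuracy limit for FHR is "95% LoA for FHR within +/- 10 bpm", accompanied by a regression of bias on magnitude.

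No section mentions confusion of maternal and fetal rates, or uses MHR to screen FHR.

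**The concern.** Reliability implies that the number shown is the fetal rate. The endpoint asks only whether there is a number. MFM-Pro separates fetal and maternal signals taken from the same abdominal electrodes, so a maternal rate appearing in the fetal channel is a possible failure on the plan's own description. A percentage of time present cannot reveal that failure, and credits it. Of two devices with the same unusable stretch, one that shows the mother's rate scores higher than one that shows nothing.

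The between-device comparison could therefore favour the device that is wrong more often. Both devices supply MHR, so the plan already collects what is needed to look for this but does not say it will be used.

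**Working it through.** **No figure to reproduce.** The documents give no expected percentage, threshold or sample-size basis for this endpoint, and no rate of maternal pick-up. What follows illustrates size only.

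**1. Effect on the percentage.** Input from the plan: a 45-minute measurement, taken as the denominator.

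Inflation = minutes of maternal rate shown as FHR / 45.

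| Maternal minutes (assumed) | Inflation, percentage points |
|---|---|
| 0.45 | 1.0 |
| 1 | 2.2 |
| 2.25 | 5.0 |
| 4.5 | 10.0 |
| 9 | 20.0 |

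Example: an FHR shown for 40.5 minutes scores 40.5/45 = 90%. If 4.5 of those minutes are maternal, the fetal share is 36/45 = 80%. Equally, a device that is right for 40.5 minutes and shows the mother for the other 4.5 scores 100%; one that blanks those 4.5 minutes scores 90%.

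**2. Does the primary analysis already catch it?** Let p be the share of paired samples in which one device alone shows the maternal rate, d the fetal-maternal gap, and s the SD of the remaining differences. With differences taken as MFM-Pro minus CTG and MFM-Pro in error, the limits are

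−p·d ± 1.96·√(s² + p(1−p)d²).

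The plan gives none of p, d or s. Assume d = 55 bpm and s = 3 bpm. For p = 1%: mean −0.55; SD = √(9 + 55² × 0.01 × 0.99) = 6.24; limits −12.8 to +11.7 bpm.

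| p | Limits, bpm |
|---|---|
| 0 | −5.9 to +5.9 |
| 0.5% | −9.9 to +9.3 |
| 1% | −12.8 to +11.7 |
| 5% | −27.0 to +21.5 |

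Setting p·d + 1.96·SD = 10 gives p ≈ 0.0052, or 0.0052 × 2700 s ≈ 14 s per 45 minutes on average. The range is p ≈ 0.0019 (d = 70, s = 4) to p ≈ 0.0124 (d = 40, s = 2). If the CTG is the device in error, the limits are mirrored.

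So pick-up on one device alone would show in the primary result. Three things remain uncovered:

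- The size of the limits does not identify the device in error.
- Maternal-rate time while the other device is blank forms no pair, so it leaves the limits untouched but still raises the percentage.
- If both devices show the mother, the pair agrees about as closely as their maternal readings do, and the limits look better than they should.

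These figures also assume pooled sample-level pairs. The plan does not state the unit of the Bland-Altman analysis, and averaging over epochs or subjects would change them.

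**3. Do the other elements cover it?** The bias regression does not use simultaneous MHR. The signal-quality confusion matrix concerns MFM-Pro alone, and its recording-quality standard is undefined. The setup check asks only whether the CTG captures the signals. The live display lets the researcher spot setup problems and annotate events, but has no rule for rate confusion and does not alter the percentage.

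**The case against.** The strongest reply is that the plan contains no rule that any displayed value counts. Taken literally, a maternal rate is not an FHR; the text is a summary; and a valid-sample definition is a detail that summaries often leave out. This stands in part. Presence-only is the plain reading of an unqualified endpoint, not an explicit instruction, and the remedy starts by saying what is counted.

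Next, the documents report no frequency of confusion, do not say which device is prone to it, and do not say how the CTG obtains MHR. That stands in full: the size and direction of any bias are unknown.

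Third, the endpoint is exploratory and has no threshold, and accuracy is tested separately by the primary limits. That also stands. A reader might infer from the figures above that the primary FHR criterion is flawed, or that a pass or fail on it would be invalid. The documents do not support that reading. The figures rest on assumed gaps, SDs and sample-level pairing, and discordant maternal pick-up would count against agreement, not go unseen. A reference error charged to the new device is a general limitation of comparing with an imperfect reference.

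Last, redefining the headline percentage with an MHR flag could remove correct data: if one device's MHR channel shows the fetal rate, the other device's correct FHR would be flagged. This is a good reason to report the flag beside the percentage and leave the percentage itself unchanged.

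**Conclusion.** The point holds as an inexpensive improvement to an exploratory endpoint, not as an error in the primary analysis. As written, the comparison labelled reliability measures availability, and each minute of maternal rate shown as FHR would add 2.2 percentage points to the score of the device showing it. This rests on the plain reading of the endpoint and on a 45-minute denominator. How often it would happen, and which device it would favour, cannot be told from the documents. The primary limits are a partial safeguard: they respond to discordant pairs, but not to unpaired or shared maternal-rate time, and they do not attribute the error to a device. A reader might also infer that the reliability comparison is biased towards MFM-Pro; nothing in the documents shows that.

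**What to change.** 1. Keep the percentage with an FHR as stated, over the same 45-minute denominator for both devices, and define what counts as an FHR sample.
2. Prespecify a flag for FHR time that coincides with simultaneous MHR within a fixed tolerance and minimum duration. The sponsor should justify the values; 5 bpm for at least 10 s is only an example. State which device's MHR raised each flag.
3. Beside the percentage, report per device: the flagged percentage, the percentage after excluding flagged time, and the percentage of time with no MHR to check against.
4. Leave the primary limits of agreement on all pairs. Add a sensitivity analysis with flagged pairs removed, split by flagged on CTG only, on MFM-Pro only, or on both.

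The cost is analysis-plan wording and a script run on tracings already stored; no extra subjects, visits or measurements are needed. The downside is that genuine overlap of fetal and maternal rates, or an MHR channel showing the fetal rate, will sometimes be flagged. A flag therefore marks possible confusion and is not proof, and the percentage after exclusion should be read with that in mind. Setting the rule in advance matters, because blaming the reference after a failed criterion would carry little weight.

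### The signal quality check is evaluated only by a confusion matrix with no stated quality metric or class boundary; the planned continuous FHR percentage should be reported by check result beside it

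*Combined protocol and SAP*

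**What the plan says.** All references are to the Clinical Investigation Plan Summary.

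- **Objectives (exploratory):** "To study the correlation between the Bloomlife MFM-Pro signal quality check result and fetal heart rate quality". No coefficient, test or target is named.
- **Endpoints (exploratory):** "Confusion matrix between the signal quality check result (pass or fail) and the recording quality", qualified by "for the MFM-Pro fetal heart rate signal, over the complete measurement". This fixes the signal and the time window. It does not fix a quality metric, the number of classes or a boundary between them.
- **Endpoints (exploratory), separate item:** "Percentage of a recording with a FHR for Bloomlife MFM-Pro and for CTG". This is continuous for each recording and is not linked to the check.
- **Statistical Data Analysis:** covers the limits of agreement and the regression of bias on magnitude. It is silent on this endpoint.
- **Number of subjects:** "Pilot phase: up to 200 enrolled subjects" and "Pivotal phase: up to 60 enrolled subjects". The objective is not tied to either phase.
- **Enrolment criteria:** a participant counts as enrolled once she is eligible and "the signal validation screening test (performed by the Bloomlife MFM-Pro) gives a successful result".
- **Study Procedures:** the device "performs an electrode connection check and signal quality check (screening test"). The 45-minute measurement then depends on the electrode connection check and the CTG setup; the signal quality check is not named as a condition.

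**The concern.** The check result is binary by nature; recording quality is not. Putting quality into classes treats a recording just below the boundary like one with almost no FHR. With the boundary open, the accuracy figures that readers take from a confusion matrix can be moved by choosing it late. This is the only endpoint that shows whether a pass predicts a usable recording, and a successful screening result is part of the enrolment definition. If the figures are to describe the check and not the chosen boundary, metric and boundary must be fixed in advance, and the ungraded data should be shown as well.

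A second difficulty sits underneath. Any assessment of the check needs recordings from women who failed it, and the document is not consistent on whether these exist in the analysed set.

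**Working it through.** **No plan figure to reproduce.** The documents give no alpha, power, effect size, fail rate or boundary for this endpoint. Everything below except the 60 and 200 rests on assumed inputs and is illustration only.

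**1. How far the boundary moves the matrix when the check is useless.** Assume quality = 100·Φ(0.9z + 1.2), with z standard normal. The mean is Φ(1.2/√(1 + 0.81)) = Φ(0.892) ≈ 81%. With no association, the share of passes called good at cut q is 1 − Φ((Φ⁻¹(q) − 1.2)/0.9).

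- Cut 50%: (0 − 1.2)/0.9 = −1.333, so 1 − Φ(−1.333) = 0.91.
- Cut 95%: (1.645 − 1.2)/0.9 = 0.494, so 1 − Φ(0.494) = 0.31.

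An uninformative check can thus be described as having 91% or 31% of its passes good. The fail row would show the same shares, so the full matrix reveals the lack of association; a predictive value quoted alone does not.

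**2. The same with a real association.** Second assumed model: normal quality score, 20% fails, fails lower by 0.8 SD, cut moved from the 10th to the 50th percentile.

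| Quantity | 10th percentile | 50th percentile |
|---|---|---|
| Poor recordings flagged fail | 0.48 | 0.30 |
| Good recordings passed | 0.83 | 0.90 |
| Fails that are poor | 0.24 | 0.74 |
| Passes that are good | 0.93 | 0.56 |

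Across the cuts examined (10th, 20th, 30th and 50th percentiles) the phi coefficient stays within 0.23–0.26. The boundary drives the accuracy figures far more than the strength of association.

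**3. Information lost by cutting.** For a normal score cut at percentile c, the asymptotic relative efficiency is φ(z_c)²/[c(1 − c)]. At the median this is 0.3989²/0.25 = 0.64. It is 0.58 at the 30th percentile, 0.49 at the 20th and 0.34 at the 10th.

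**4. The same loss expressed as detection rate.** This uses the step 1 model with z shifted by −1 in check-fails and two-sided 0.05 (tests added for illustration; the plan has none). At an 80% cut the threshold is (0.842 − 1.2)/0.9 = −0.398, so 34.5% of passes are poor (Φ(−0.398)) against 72.6% of fails (Φ(0.602)).

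| Fails of 60 | Fisher exact, 80% cut | Rank-sum, continuous |
|---|---|---|
| 6 | 0.35 | 0.57 |
| 10 | 0.55 | 0.77–0.79 |
| 15 | 0.71 | 0.90 |

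At 200 women and 10–25% fails, the same shift gives 0.91–0.999 against 0.98–1.00, so little gap is left. With a shift of 0.5 the gap remains: 0.38–0.66 against 0.55–0.85.

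The second model agrees in direction: at 60 women, 20% fails and 0.8 SD, 0.65 with continuous quality against 0.39–0.43 after a cut.

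**5. Searching for a boundary.** With no association and 60 women, taking the smallest Fisher p-value over ten cuts (50%, 55%, …, 95%) gives p < 0.05 in 10–14% of studies for 6–15 fails, against 4–5% for the rank test.

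**6. Whether there is a fail group.** Under Enrolment criteria, enrolled women have a successful screening test. Study Procedures places the signal quality check within that test. If only enrolled women are analysed, the number of fails is 0: the matrix has one empty row and the continuous comparison has one empty group. Study Procedures, however, lets measurement proceed without naming the signal quality check, which would allow check-fail recordings to exist. The two rows cannot both be applied without a stated analysis set.

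**The case against.** The case for the plan is substantial, and much of it stands.

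- **The endpoint is descriptive and exploratory.** A reader might infer that the trial loses statistical power or risks a false positive finding. The documents do not support that: no test, alpha or success criterion is attached to the matrix. The detection rates above only scale the loss of information.
- **A confusion matrix suits a pass/fail check.** How often a pass yields an acceptable recording is the practical question, and the word correlation in the objective may simply mean association. The matrix should stay.
- **Two classes, and quality measured as FHR percentage, are inferences.** Only the check is stated to be binary. Quality could be graded in another way.
- **The document is a summary.** A fuller plan may define metric and boundary.
- **Part of the gap at 60 women is not due to cutting.** Fisher's test is conservative here: it rejects in 2.5–4% of null studies at the 80% cut, against 4–6% for the rank test.
- **The pilot allows up to 200 women.** At that size the gap is small for a large shift. This answers only part of the point, since the gap persists at a 0.5 shift.

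None of this supplies the missing metric and boundary, or explains why the percentage already planned is not set against the check result.

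**Conclusion.** The point holds as a cheap improvement to an exploratory analysis. Metric and class boundary are not stated, so sensitivity and predictive values rest on a choice still open when the data arrive, and grading within classes is lost. At 60 women with 10 fails and a 1-unit latent shift, the loss corresponds to about 55% detection at a fixed 80% cut against about 77–79% with continuous quality. That size depends entirely on the assumed fail count, quality distribution and effect.

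A reader might go further and infer that the boundary decides the result. That is too strong: predictive values move widely, but the association measure was nearly stable across the cuts examined. Nor do the documents suggest that anyone intends to choose the boundary after the fact; they only leave that possible.

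Both the matrix and the continuous comparison need check-fail recordings, and the document leaves their inclusion unresolved. No primary or secondary conclusion is affected.

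**What to change.** 1. Keep the confusion matrix. Define recording quality and one class boundary before the pivotal data are opened, and report sensitivity, specificity and predictive values with confidence intervals.
2. Add the planned percentage of the 45-minute measurement with an MFM-Pro FHR, compared between check-pass and check-fail recordings: medians, the difference with a 95% CI, and the area under the ROC curve.
3. State that this analysis uses all measured participants, including check-fails, and which phase or phases supply the data.
4. Reconcile Enrolment criteria with Study Procedures on whether women who fail the signal quality check are measured and analysed. If no check-fail recordings will exist, say that the objective cannot be answered by either analysis.

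The cost is a few sentences and one more table row. If check-fail women are measured, no new data are needed. The small downside is a less simple headline than a single sensitivity and specificity pair.

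### The exploratory reliability comparison is conditional on set-up success, and the set-up filter differs between CTG and MFM-Pro

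*Combined protocol and SAP*

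**What the plan says.** All references are to the Clinical Investigation Plan Summary in the combined protocol and SAP.

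- **Objectives (exploratory).** One objective is "To compare measurement reliability of Bloomlife MFM-Pro and CTG in measuring fetal heart rate". A parallel one covers maternal heart rate.
- **Endpoints (exploratory).** The matching endpoints are "Percentage of a recording with a FHR for Bloomlife MFM-Pro and for CTG" and "Percentage of a recording with a MHR for Bloomlife MFM-Pro and for CTG". Neither has a threshold or a test attached.
- **Study Procedures, set-up.** Both devices collect data for as long as 15 minutes while MFM-Pro runs its electrode connection check and its signal quality check. On failure: "If the electrode connection check fails or the CTG does not capture the MHR/FHR signals, the measurement setup is adjusted as needed", and "up to three attempts are allowed".
- **Study Procedures, study measurement.** The 45 minutes follow under a condition: "If the electrodes connection check and the CTG setup are successful, data is collected with both the Bloomlife MFM-Pro and the CTG monitor".
- **Enrolment criteria.** A woman counts as enrolled only once MFM-Pro's own screening of the signal has succeeded.
- **Endpoints (last exploratory item).** Passes and failures of the signal quality check are cross-tabulated with the quality of the MFM-Pro fetal heart rate signal over the whole measurement.

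The document does not define *recording* or name an analysis set for the reliability endpoints. It does not say whether set-up data count, how a woman whose set-up finally fails is scored, or whether such failures are reported by device.

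**The concern.** A reliability comparison should answer how often each device delivers a heart rate when it is applied to a woman. A woman in whom CTG cannot pick up the fetal heart rate after three attempts is the clearest CTG reliability failure there is. Under the Study Procedures she does not go on to the 45 minutes, so neither device has a 45-minute trace from her. The same holds for a woman whose electrode connection check never passes.

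For CTG, then, entry to the measurement depends on the outcome that the measurement is meant to compare. For MFM-Pro it depends on a technical precondition of that outcome. Two devices that have passed different filters are then set against each other on one percentage. If they fail set-up at different rates, the difference in the 45-minute percentages can misstate the difference among all women to whom both were applied. A reader could also take the percentages as applying to all those women, when they apply only to women in whom both set-ups succeeded.

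**Working it through.** The plan states no set-up failure rate, no expected percentage and no derivation for these endpoints, so there is no figure to reproduce. The check is a comparison of the text, followed by an illustration on assumed values.

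**1. What each device must pass before the 45 minutes**

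| | CTG | MFM-Pro |
|---|---|---|
| Study Procedures | has captured maternal and fetal heart rate | electrode connection check passed |
| Enrolment criteria | nothing | screening test successful |
| Related to the endpoint? | yes, it is the same outcome | contact only under Study Procedures; also signal if enrolment defines the analysis set |

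The two MFM-Pro rows do not fit together. The condition for starting the measurement does not name the signal quality check, and the cross-tabulation endpoint needs women who failed that check to have been measured. The enrolment criterion points the other way, because Study Procedures attaches the screening-test label to the step that contains both checks.

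**2. Illustration of scale (all rates assumed)**

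Let p be the mean percentage with a fetal heart rate in women in whom the device was set up, equal for both devices. Let f_M and f_C be the shares of women in whom MFM-Pro and CTG finally fail set-up. Score a failed set-up 0% for the device that failed. The percentage over all women attempted is p × (1 − f), and the gap hidden by a conditional difference of 0 is p × (f_M − f_C).

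| p | f_M | f_C | MFM-Pro, all attempted | CTG, all attempted | MFM-Pro minus CTG |
|---|---|---|---|---|---|
| 90% | 10% | 3% | 90 × 0.90 = 81.0 | 90 × 0.97 = 87.3 | −6.3 |
| 90% | 3% | 10% | 87.3 | 81.0 | +6.3 |
| 90% | 5% | 2% | 90 × 0.95 = 85.5 | 90 × 0.98 = 88.2 | −2.7 |
| 90% | 5% | 5% | 85.5 | 85.5 | 0 |

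If only one device fails, in 10% of women, the shift is 80 × 0.10 = 8.0 points at p = 80% and 95 × 0.10 = 9.5 points at p = 95%.

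**3. How many women this could concern**

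Take 60 measured women, the upper limit for the pivotal phase, as an assumption; the plan's 60 counts enrolled women. The number to attempt is 60 / (1 − f), where f is now the share of women in whom either set-up finally fails.

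- f = 5%: 63.2, so 64 attempted and 4 without a 45-minute trace.
- f = 10%: 66.7, so 67 attempted and 7 without.
- f = 20%: 75 attempted and 15 without.

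**4. Effect on the device that worked**

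Let q be the MFM-Pro percentage in women whose CTG set-up failed, and suppose MFM-Pro set-up succeeds in all women. Its percentage over all women attempted is (1 − f_C) × p + f_C × q = p + f_C × (q − p). Removing these women raises the MFM-Pro figure if q < p and lowers it if q > p. The plan gives no information on q. The table in step 2 takes q = p.

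**The case against.** Several stronger readings are tempting, and the documents do not support them.

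- **That women in whom either device cannot obtain a signal are excluded.** This is explicit for CTG only. A woman with good electrode contact but poor fetal heart rate extraction can go on to the 45 minutes under Study Procedures, where she lowers the MFM-Pro percentage.
- **That set-up failures are missing from both percentages.** This is an inference. *Recording* is undefined, both devices collect data during set-up, and the adverse-event text in Study Procedures treats the check and the measurement together as data collection. What is established is that these women have no 45-minute recording and that no rule covers them.
- **That both percentages are inflated.** This does not follow for the device that worked, as step 4 of the working shows.
- **That the comparison favours a particular device.** No failure rates are given. With equal rates the illustrated gap is 0.

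It can also be said that the share of a recording with a heart rate is a legitimate measure of signal continuity, that set-up success is a separate quantity, and that combining them with zeros is a choice of estimand. That is fair, and it is why the combined analysis should be supplementary. Scoring the working device from a trace of at most 15 minutes, possibly taken during readjustment, mixes unlike periods with the 45-minute recordings. Finally, the document is a summary and the eCRF is not shown, so attempts and failures may already be logged. What remains is that the stated objective is a comparison of reliability, and nothing in the plan states the condition on the result or calls for set-up failures to be reported by device.

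**Conclusion.** The point holds as a limit on what the two exploratory reliability objectives can conclude. The 45-minute percentages are conditional on set-up success, with CTG selected on the outcome itself and MFM-Pro on electrode contact, or also on signal if the enrolment criterion defines the analysis set. The comparison can be biased if set-up failure rates differ. Its direction and size cannot be derived from the documents. The 6.3 and 2.7 points rest on an assumed 90% for both devices, on assumed failure rates, on a score of 0% for the failed device, and on the working device performing as usual in the same women.

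The endpoints are exploratory and carry no decision rule. The primary limits of agreement are not affected by this point. A clarification and one added analysis are proportionate.

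**What to change.** 1. Define *recording*, including whether set-up data belong to it, and define the reliability population. Reconcile the Enrolment criteria with the Study Procedures and the cross-tabulation endpoint on whether women who fail the signal quality check are in it.
2. For all consented women on whom both devices were applied, tabulate by device the number of attempts used and the number whose set-up finally failed.
3. Add a supplementary reliability analysis in that population, with a failed set-up scored 0% for the device that failed. Use set-up-phase data for the other device only in a sensitivity analysis labelled as such.
4. State beside the 45-minute percentages that they apply only to women in whom both set-ups succeeded.

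Cost: no new procedure, one extra table, and an attempt and failure field per device in the eCRF if it has none. The exploratory figures may look less favourable.
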